5.4.2 Clinical

5.4.2.1 Feasibility

Feasibility to use propranolol in autologous MM HCT recipients for the adjunct cancer control purposes will be determined by a 55-70% enrollment rate and 65-70% retention rate as described in section 3.2.2.1. The rates of these events will be tabulated.

5.4.2.2 Outcomes

- Depression and anxiety: HADS scores will be tabulated and evaluated comprehensively as well as by HADS-A and HADS-D. The trajectory of these scores over the course of the study will be described. Differences in scores between the treatment vs. control groups over the course of the study will be assessed.
- Engraftment syndrome: Engraftment syndrome occurrences will be tabulated and the incidence described for both treatment and control arms.
- Neutrophil engraftment: Differences in time to neutrophil engraftment will be determined between treatment and control arms.
- Platelet engraftment: Differences in time to platelet engraftment will be determined between treatment and control arms.
- Infection: Infection events will be tabulated and differences in events will be determined for treatment and control arms.
- Response to treatment: The rates of VGPR or better (nCR, CR, and sCR) will be calculated at 100 days post-transplant and compared between intervention and control arms.
- Treatment-Related Mortality (TRM): TRM is defined as death occurring in a patient from causes other than disease progression. Disease progression is a competing event for TRM. The time to this event is the time from randomization to death, disease progression, loss to follow-up or the end of 100 days post-transplant, whichever comes first. Patients alive without disease progression at 100 days are considered censored. The cumulative incidence of TRM at 100 days will be estimated separately for each treatment-group. Overall TRM through 100 days of follow-up will be compared using Gray's test.
- Progression-free survival (PFS): PFS will be compared between the two arms as a time to event endpoint censored after 100 days of follow-up on each patient. Patients are considered a failure of the primary endpoint if they die or suffer from disease progression. The time to this event is the time from randomization to progression, death, loss to follow up or Day 100 - whichever comes first. The Kaplan-Meier estimate of survival will be estimated separately for each treatment group at 100 days post-transplant.
- Overall survival (OS): The event is death from any cause. The time to this event is the time from randomization to death, loss to follow-up or the end of 100 days, whichever comes first. Patients alive at the time of last observation are considered

censored. Estimates of OS will be described for each group at 100 days post-transplant. The Kaplan-Meier estimate of survival will be estimated separately for each treatment group at 100 days post-transplant. Overall survival will be compared using a log-rank test at a two-sided significance level of .05.

[figure not shown]

Figure 1. Treatment schema diagram; day values are in reference to transplant as Day 0

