2.3 Patient Eligibility

2.3.1 Inclusion Criteria

Patients with multiple myeloma receiving an autologous HCT are eligible when the following criteria are met:

1. 18-75 years of age
2. ≤ 1 year since initiation of systemic anti-myeloma therapy
3. Patient is scheduled for autologous hematopoietic stem cell transplant as the upfront therapy for their multiple myeloma
4. Karnofsky Performance Status of $\geq 80\%$; patients eligible for HCT are eligible for the study
5. All men and women must agree to practice effective contraception during the study period if not otherwise documented to be infertile.

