3.2.2.2 Outcomes

- Depression and anxiety: as assessed by the HADS, with scores of 8 or above on HADS-A (7 items) and HADS-D (7 items) defining significant anxiety or depression, respectively.⁴² Depression and anxiety will be described both overall and between treatment vs. control groups.
- Engraftment syndrome: presence of fever, diarrhea, or rash within 48 hours before or after neutrophil recovery that requires steroids for treatment. This will be determined at the discretion of the treating physician and will be categorized as yes/no.
- Neutrophil engraftment: time to absolute neutrophil count (ANC) $> 0.5 \times 10^9/\text{L}$ sustained for three consecutive assessments at least one day apart.
- Platelet engraftment: time to achieve a platelet count of (a) $> 20 \times 10^9/\text{L}$ independent of platelet transfusions for 3 consecutive assessments at least one day apart.
- Infection: number of documented culture positive infections or neutropenic fever episodes defined as fever > 100.4 degrees F.
- Response to treatment: The trial will assess the rates of very good partial response (VGPR) or better (near complete response (nCR), CR, and stringent CR (sCR)) according to the International Uniform Response Criteria at day 100 post-HCT.
- Treatment-Related Mortality (TRM): TRM is defined as death occurring in a patient from causes other than disease progression. TRM will be assessed at D100

for both the intervention and control arms. Patients alive and progression-free at 100 days will be censored.

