4.0 ENROLLMENT PROCEDURES

4.1 Patient Enrollment

Patients will be approached for this study during the pre-transplant evaluation phase. Transplant physicians will evaluate the patient eligibility onto this study. Eligible patients willing to participate in the trial will sign an MCW IRB approved informed consent form. A Clinical Trials Office CRC will record the documentation of patient consent and proceed with registration procedures. All source documents that support eligibility including a signed informed consent/HIPAA and signed eligibility checklist, will be available, reviewed and eligibility verified. At the point of registration, a member of the study team will register the patient in the electronic database, including demographics, consent and on-study information. The patient will be assigned a unique sequence number for the study. The principal investigator (PI) of the study, [name], will be notified prior to enrollment. Pharmacy will be notified upon patient registration. If at any point in time a patient wishes to withdraw from the study, they may notify [name] verbally or in writing. There will be no further data collection for participants who elect to withdraw from the study.

Target enrollment is 40 (20 per group) and includes patients undergoing autologous HCT for MM at MCW. Half of the participants will be randomized via permuted block assignment with random block sizes to receive propranolol upon study entry. Informed consent will be obtained to access participants' full medical records to ascertain relevant demographic and medical data as outlined in Section 4.2. The patient must have signed informed consent prior to registration on the study. Due to the pilot and feasibility nature of this study, the need to monitor response to prophylactic beta-blocker usage in a medically ill population, as well as the objective nature of gene expression profiling, this pilot study will not be blinded. Patients will be enrolled before study commencement at Day -7. Total study duration will be up to 7 weeks for participants assigned to the intervention group (1 week pre-transplant through 6 weeks post-transplant) and 5 weeks for those in the control arm (1 week pre-transplant through 4 weeks post-transplant). Additional clinical information will be collected for 100 days post-transplant as identified in section 3.2.2.2.

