4.2 Baseline Demographic-, Disease-, and Treatment-Related Variables

Patient-related:

- Age at transplant
- Gender
- Race: Caucasian vs. African American vs. Asian/Pacific Islander vs. Other
- Body Mass Index: <18.5 vs. 18.5-24.9 vs. 25-29.9 vs. >=30
- Smoking status in 3 months prior to HCT (Y/N)
 - Household income prior to disease diagnosis: <\$23,000, \$23,000-\$34,999, \$35,000-\$44,999, \$45,000-\$54,999, \$55,000-\$64,999, \$65,000-\$74,999, >\$75,000
- Number of individuals in patient's household
- Education level: < high school vs. high school graduate vs. some post high school education vs. college degree vs. professional degree

Disease-related:

- International Stage
- Disease status prior to transplant: complete response, very good partial response, partial response, or stable disease
- Cytogenetics: high risk vs. standard risk by International Myeloma Working Group (IMWG) criteria

Treatment-related:

- Number of CD34+ cells infused/kg of recipient body weight
- Transplant setting: inpatient vs. outpatient transplant (defined as patients who plan to stay outpatient during entire transplant period)

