5.2 Sample Size and Power Calculation

We will enroll 40 participants undergoing autologous HCT for MM at MCW. Accounting for study attrition and beta-blocker intolerance, we aim to have 30 patients with a complete set of gene data. A sample size of 40 will inform our feasibility aim, while a targeted final sample of 15 participants in the intervention group will be sufficient for gene expression analysis. The gene expression sample size is based on previous studies with similar or smaller sample sizes that have evaluated gene expression as a function of psychosocial factors and yielded hundreds of differentially expressed genes that generate statistically significant results in higher-order bioinformatics.^{35, 45, 46} More specific sample size estimates are difficult to project with any greater accuracy, as there is not data on the effect size for gene expression differences as a function of propranolol in humans. To this end, the current proposal will inform future sample size estimations. This study is intended mainly to generate effect size estimates and 95% confidence intervals to aid with planning future research projects. We will generate both simple estimates of effect size as well as adjusted estimates, attempting to control for any accidental confounding that may occur despite randomization.

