Primary analyses will be performed at the time of all 3 blood draws (Baseline, Day -2, and Day +28) and will use general linear model analyses to quantify the association between expression of each of the 53 CTRA contrast genes and beta-blocker usage. To ensure analysis of patients with sufficient beta-blocker exposure, only gene expression data from study participants with an adherence rate of 80% (at either dose) will be used as comparators against the control group. Descriptive tables of patient-, disease-, and transplant-related factors will be prepared with separate columns by propranolol vs. no propranolol groups. Any demographic or psychosocial variables (other than those of primary interest) that are unevenly distributed between groups after randomization will be adjusted for in subsequent analyses as previously described using ANCOVA. Further, differences in gene expression will be compared between groups/variables that might not have been randomly distributed, regardless of beta-blocker treatment assignment, to ascertain whether these differences may be stronger than drug-attributed changes. The UCLA Social Genomics core will provide genetic and statistical analyses for gene expression data.

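### The Day 100 response comparison ignores the recorded pre-transplant disease status, so patients already at VGPR or better dilute any effect on conversion and add avoidable noise

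*Combined protocol and SAP*

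**What the plan says.** Objective 2b in section 2.2 lists myeloma response among the clinical endpoints to be described by arm. Section 3.2.2.2 defines it as attained status at Day 100: "The trial will assess the rates of very good partial response (VGPR) or better". Section 5.4.2.2 gives the analysis: "The rates of VGPR or better (nCR, CR, and sCR) will be calculated at 100 days post-transplant and compared between intervention and control arms". Neither section mentions status before transplant, and no test or interval is named.

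That status is nevertheless collected. Section 4.2 lists "Disease status prior to transplant: complete response, very good partial response, partial response, or stable disease", and Table 4.7b places disease-related variables at the baseline visit. Two of the four categories already satisfy the Day 100 definition. Section 2.3.1 admits patients up to one year "since initiation of systemic anti-myeloma therapy", and section 2.3.2 does not exclude those who have reached CR or VGPR.

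On balance and adjustment, the plan has four pieces of text:

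- Section 4.1: patients are "randomized via permuted block assignment with random block sizes to receive propranolol upon study entry". No stratification factor is stated.
- Section 5.2: adjusted as well as simple effect estimates are promised, to deal with chance confounding left after randomisation. No covariate is named.
- Section 5.3.1, on gene expression: "Any demographic or psychosocial variables (other than those of primary interest) that are unevenly distributed between groups after randomization will be adjusted for". Disease status is neither demographic nor psychosocial.
- Section 5.3.1 also requires disease-related factors to be tabulated by arm.

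**The concern.** A patient who enters at VGPR or better and keeps that response is a success in either arm, at a level reached before propranolol began. Such patients cannot show conversion. The more of them there are, the smaller the visible difference for a given drug effect on the rest.

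Entry status is also likely to be a strong predictor of Day 100 status. With 20 per arm and no stratification, the arms can differ in it by chance, and the raw comparison carries that difference straight into the result. Section 5.2 says the study is mainly meant to supply effect sizes and 95% confidence intervals for planning later work. A diluted estimate with removable noise serves that purpose less well than the data allow.

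**Working it through.** The plan gives no response rate, effect size or power for this outcome, so there is no figure to reproduce.

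**Inputs.** From the documents: 20 per arm (section 4.1). Assumed, because the documents do not give them: entry share at VGPR or better b = 0.3 to 0.6; conversion among the rest c = 0.4 on control and 0.6 on propranolol; everyone who enters at VGPR or better is still there at Day 100.

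**Dilution.** The Day 100 rate is b + (1 − b)c, so the arm difference is (1 − b) × (0.6 − 0.4).

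| b | Control | Propranolol | Difference |
|---|---|---|---|
| 0.3 | 58% | 72% | 14 points |
| 0.5 | 70% | 80% | 10 points |
| 0.6 | 76% | 84% | 8 points |

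**Chance imbalance.** The numbers entering at VGPR or better are two independent Binomial(20, b) counts. The probability that they differ by 3 or more is 0.387, 0.420, 0.430 and 0.420 for b = 0.3, 0.4, 0.5 and 0.6. Each surplus patient replaces one who would have converted with probability c, so a 3-patient gap shifts the difference by 3/20 × (1 − c): 9 points at c = 0.4 and 6 points at c = 0.6. That is of the same order as the diluted effect.

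**How much outcome variation entry status explains.** With p the overall rate, the share is b(1 − b)(1 − c)² / [p(1 − p)]. At c = 0.4:

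- b = 0.3: 0.21 × 0.36 / (0.58 × 0.42) = 31%.
- b = 0.6: 0.24 × 0.36 / (0.76 × 0.24) = 47%.

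**What adjustment gains.** Approximate 95% half-widths are 1.96 × √variance. Here 0.48 = 0.4 × 0.6 + 0.6 × 0.4.

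- Raw difference, variance [p₀(1 − p₀) + p₁(1 − p₁)]/20. At b = 0.3: (0.2436 + 0.2016)/20 = 0.0223, half-width 29 points. At b = 0.6: (0.1824 + 0.1344)/20 = 0.0158, half-width 25 points.
- Stratified by entry status, variance (1 − b) × 0.48/20. At b = 0.3: 0.0168, half-width 25 points. At b = 0.6: 0.0096, half-width 19 points.
- Conversion only, 20(1 − b) patients per arm. At b = 0.3: 0.48/14 = 0.0343, half-width 36 points. At b = 0.6: 0.48/8 = 0.06, half-width 48 points.

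Stratifying therefore removes noise from the overall difference, which stays at 14 to 8 points. Only the conversion rate shows the undiluted 20 points, and it does so imprecisely.

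**Power, for scale** (two-sided 0.05 assumed; the plan states that level only for overall survival). At b = 0.3, 0.5 and 0.6, power is 15%, 11% and 9% for the raw comparison and 18%, 14% and 12% for conversion alone.

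**The case against.** The strongest reply is that nothing here is biased. The arms are randomised, so without a drug effect the expected difference is zero whatever the entry share. Chance imbalance in a prognostic factor is part of the sampling variation that an interval for the raw difference already covers. This is correct. The 39% to 43% figure describes noise and is not a separate validity defect. What remains is that part of the noise can be removed with a variable already on file.

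Second, section 5.2 promises adjusted estimates, and the by-arm tables in section 5.3.1 would expose an imbalance. Both are true, but the promise names no covariate and a table does not correct an estimate.

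Third, the outcome is secondary and descriptive, no primary or feasibility conclusion rests on it, and a conversion-only analysis is less precise than the raw one. All of that stands. It is why the stratified estimate should carry the comparison, with conversion as description.

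A reader might go further and infer that the outcome is settled before the first dose for patients entering in VGPR or CR. The documents do not support that: such a patient can progress or die by Day 100, so an effect on keeping a response would still be counted.

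**Conclusion.** The point holds as a low-cost improvement to a secondary outcome. The raw comparison is unbiased but less informative than it could be. Under the assumed rates, a 20-point conversion effect is seen as 14 to 8 points, and ignoring entry status leaves the 95% half-width at about 25 to 29 points where about 19 to 25 is attainable. These sizes rest on assumed entry and conversion rates and on full maintenance of response among those who enter at VGPR or better.

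It is tempting to conclude that the Day 100 outcome largely reflects earlier therapy and not propranolol. That is not established. Carried-over responders form the majority of control-arm responders only if b exceeds c/(1 + c), which is 0.23, 0.29 and 0.33 for c = 0.3, 0.4 and 0.5, and the documents do not give b. Even where it does, the statement concerns the rate within an arm. The difference between arms still carries the drug effect, diluted and not removed.

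**What to change.** In sections 3.2.2.2 and 5.4.2.2:

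1. Make the between-arm response estimate stratified by, or adjusted for, pre-transplant status as recorded at baseline (VGPR or better versus less), with a 95% confidence interval. A stratified risk difference such as Mantel-Haenszel suits these numbers: nearly everyone in one stratum may be a responder, which can make a logistic model fail to converge.
2. Cross-tabulate Day 100 response by pre-transplant status within each arm.
3. Report conversion to VGPR or better among patients below it at entry, and the raw rate, as descriptive.
4. Name pre-transplant status as a covariate for the adjusted estimates promised in section 5.2.

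The cost is wording only, since the variable is already collected. The conversion rate will rest on about 8 to 14 patients per arm under the assumed entry shares and should be presented as imprecise. The text should also say that no version of this comparison tests efficacy with 40 patients: for the illustrated effect, 80% power would need 182 to 392 per arm on the raw rate, or 97 patients below VGPR at entry per arm on conversion.

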APPENDIX A
DRUG INTERACTIONS

Appendix A: Full list of concomitant medications to be used with caution

Abiraterone Acetate	Lopinavir
Afatinib	Methotriimeprazine
Alfuzosin	Methoxsalen (Systemic)
Amifostine	Methyldopa
Aminophylline	Methylergonovine
Brimonidine (Ophthalmic)	Mexiletine
Bromocriptine	Norepinephrine
Bupropion	Norepinephrine
Cabergoline	Obinutuzumab
Carbamazepine	Ofloxacin (Systemic)
Cinacalcet	Paroxetine
Ciprofloxacin (Systemic)	Phenobarbital
Clonidine	Phenoxybenzamine
Cocaine	Phentolamine
Colchicine	Prazosin
Dopamine	Primaquine
Doxorubicin	Primidone
Dabigatran Etexilate	Rituximab
Delavirdine	Rifampin
Dexmedetomidine	Ritonavir
Dihydroergotamine	Rivaroxaban
Doxazosin	Rizatriptan
Dronedarone	Stiripentol
Dyphylline	Silodosin
Epinephrine (Racemic, Systemic, Oral Inhalation, Nasal)	Tamsulosin
Ergoloid Mesylates	Terazosin
Ergonovine	Terbinafine (Systemic)
Ergotamine	Theophylline
Everolimus	Thiabendazole
Fluoxetine	Thioridazine
Fluvoxamine	TiZANidine
Grass Pollen Allergen Extract (5 Grass Extract)	Tipranavir
Guanfacine	QuiNIDine
Isomethcptene	Vemurafenib
Levonordefrin	Vincristine

APPENDIX B
ADVERSE EVENT REPORTING

Introduction

Clinical trials that assess interventions in the setting of hematopoietic cell transplantation is challenging as the number of expected AEs is high. The Blood and Marrow Transplant Clinical Trial Network (BMT CTN) has established an AE capture approach specific for transplant trials. This approach has the objective of optimizing the capture of AEs by reducing the noise-signal ratio and identifies AEs that are not expected after transplant or overlaps with manifestations of common complications, such as GVHD or graft failure.

Definitions

Adverse Event (AE) - Any untoward medical occurrence in a patient or clinical investigation subject administered a pharmaceutical product, medical treatment or procedure and which does not necessarily have to have a causal relationship with this treatment. An AE can be considered therefore to be any unfavorable and unintended sign (including an abnormal laboratory finding, for example), symptom, or disease temporally associated with the use of a medicinal product, medical treatment or procedure whether or not related to the medicinal product. AEs are expected in the HCT population.

Expectedness: An adverse event can be Expected or Unexpected

- **Expected adverse events** are those that have been previously identified as resulting from administration of the agent. For the purposes of this study, an adverse event is considered expected when it appears in the current adverse event list, the Investigator's Brochure, the package insert or is included in the informed consent document as a potential risk.
- **Unexpected adverse events** are those that vary in nature, intensity or frequency from information in the current adverse event list, the Investigator's Brochure, the package insert, or when it is not included in the informed consent document as a potential risk.

Life-threatening Adverse Event – Any adverse event that places the patient or subject, in view of the investigator or treating physician, at immediate risk of death from the reaction. Study toxicities are graded using the adapted NCI Common Toxicity Criteria (where appropriate use the criteria for transplant patients.)

- **Serious Adverse Event (SAE)** – Any adverse event occurring that results in any of the following outcomes:
 - death – regardless of cause
 - life-threatening adverse event (see above)
 - persistent or significant disability/incapacity
 - congenital anomaly
 - requires intervention to prevent permanent impairment or damage

AE Grading: All AEs that occur in this protocol will be graded according to the NCI Common Terminology Criteria for Adverse Event (CTCAE) v 4.0.

AE Reporting: Depending on the type, severity and whether it is expected, each AE will need to be reported in an appropriate timeline to MCW IRB, Data Safety and Monitoring Committee and FDA (if applicable for studies under an Investigational New Drug [IND] protocol).

Adverse Events Reported to the DSMB

All adverse events that are classified as grades 3 to 5 will be reported to the DSMC. The differences are the timing and amount of information associated with each.

The two-tier approach collects adverse events at specific time points during the trial (calendar-driven) and event-driven upon knowledge of an event deemed serious (grades 3 to 5) or unexpected to be seen in a transplant setting.

Grades 3-5 Adverse Events

For the calendar-driven collection of toxicity, the protocol mandates collection of toxicity on a form that captures most of the most important toxicities observed post transplant. The forms would capture all the AEs that occur in a preceding period, for example day 28 toxicity form, collects all the AEs that occurred from enrollment to day 28 and the grade of each AE. This first period includes all non-hematologic toxicity, since it is expected significant hematologic toxicity will occur immediately post transplant as an effect of the transplantation. Hematologic toxicity will be capture when it occurs beyond day 28 post transplant.

Unexpected Grades 3-5

The threshold for collection of adverse events outside the calendar forms is related to the grade (grades 3-5) and expectedness related to the transplant procedure or possibly related to the study drug. These events are required to be reported to the DSMC in a more immediate time frame and also require more information. For any adverse event that meets these criteria, the report would require a narrative of the event, associated laboratory and imaging information, associated medications and any relevant source documents. These reports are uploaded into Oncore and we will notify the DSMC chair and MCW IRB within 24 hours or 3 to 5 calendar days depending on the severity of the event. Both the PI and the CTO BMT Section leader will be responsible to review and determine if an event meet criteria prior to uploading it in Oncore.

Reporting timelines:

1. **Fatal (grade 5) or Life Threatening** events must be reported within 24 hours but not later than 3 calendar day of the investigator's observation or awareness of the event.
2. **All other events grades 3-4 unexpected** events (non-fatal/non life-threatening) must be reported within 3 to 5 calendar days of the investigator's observation or awareness of the event.

The proposed method outlined here follows the same requirements from MCW IRB for prompt reporting of an event or **Unanticipated Problem Involving Risks to Subjects or Others (UPIRSO)**: which is defined as any incident, experience, or outcome that meets all of the following criteria:

1. Unanticipated (in terms of nature, severity, or frequency) given (a) the research procedures described in the protocol-related documents, such as the IRB-approved research protocol and informed consent document, instructions for Use/Device Manual and or Investigator's Brochure; and (b) the characteristics of the subject population being studied;
2. Related or possibly related to participation in the research (in this guidance document, possibly related means there is a reasonable possibility that the incident, experience, or outcome may have been caused by the procedures involved in the research) or test article; and
3. Suggests that the research places subjects or others at a greater risk of harm (including physical, psychological, economic, or social harm) than was previously known or recognized.

DSMC Reporting

The table below summarizes the reporting practices from the study to the DSMC. For the ongoing review of an opened trial, the DSMC will receive a report that includes in a tabular form all the grades 3 to 5 that occurred in the trial, summarized according to reporting periods: for example 0-28d, 28-56d, 56 to 100d, 100-180d, 180-270d, 270 to 365d and 0-365d. Additionally the report will include all the unexpected grades 3-5 that occurred in trial participants since activation of the trial and lastly the number of patients who met the graft failure stopping guidelines.

For the unexpected grades 3 to 5, upon knowledge of the event, this will be discussed with the study PI and the CTO BMT section leader. If this fulfills criteria for expedited reporting to the DSMC and IRB, a narrative will be uploaded in Oncore and the DSMC will be notified, either through its secretary or directly to the Chair.

Stopping Rules

- Unexpected SAEs attributable to drug in excess of 20% would be unacceptable. If more than 2 out of the first (or subsequent) 10 participants enrolled in the trial experience a SAE resulting in life threatening complications/death, the trial will be stopped.

	All Grades 3-5	Unexpected Grades 3-5
Type of collection	Calendar-driven	Event-driven
Reporting format	Tabular or graphical format	Narrative with supporting documents
Timing of reporting	Biennial basis - cumulative	Within 3 to 5 calendar days from knowledge of the event and cumulative in a biennial basis.

References

1. Cole SW and Sood AK. Molecular pathways: Beta-adrenergic signaling in cancer. *Clinical Cancer Research*. 2012;18(5):1201-1206.
